10.5.4 Sensitivity Analyses

[figure not shown]
Sensitivity analyses will be performed for the Phase 3 portion of the study utilizing the Full Analysis Set to assess the robustness of select primary and secondary endpoints as noted below. Primary analysis method for primary efficacy endpoints as well as the secondary efficacy endpoints will be repeated for the Per Protocol Analysis Set to assess the impact of IPDs. All p-values will be descriptive.

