10.5.4.2 OS Sensitivity Analyses

The following set of analyses will be used to assess the robustness of the OS primary analysis given the potential for bias related to informative censoring, and also to assess the impact of subsequent anti-cancer therapy.

- OS potential informative censoring will be assessed with a competing risks analysis utilizing the Fine-Gray proportional subdistribution hazards model ([Fine, 1999](#); [Gray, 1988](#)) (see code fragment in [Appendix C](#)). Censoring times will be classified as (1) administrative (random) if within 140 days (corresponding to maximum lag time allowable between long term follow up assessments) of the analysis data cutoff date or otherwise (2) informative. Type (2) censoring will be defined as a competing risk event. Gray's test will be performed and the Fine-Gray treatment HR with 95% CI will be calculated stratified as per dual primary efficacy endpoints.
- The impact of subsequent anti-cancer therapy on OS will be assessed by summarizing the incidence by treatment arm of selected anti-cancer therapies with potential OS benefit, the timing of such therapies among subjects that received it, and K-M and treatment HR estimates of time to first use among all subjects. OS analyses will be repeated in which OS is censored at the first selected anti-cancer therapy.
- Since this analysis may introduce bias due to dependent censoring, the OS effect will also be estimated with an inverse probability censoring weighting (IPCW) method (see code fragment in [Appendix C](#)) that incorporates a pre-specified covariate history (eg, grouped stage of disease (not IVRS), LDH, SLD, change in ECOG performance score, *BRAF* mutation (not IVRS), PD-L1, **and** time to progression per irRC-RECIST.) and outcomes up to the start of subsequent anti-cancer therapy ([Robins et al., 2000](#))

In the event of inadvertent SUSAR unblinding, an additional sensitivity analysis for OS will be performed to assess the potential effect of the unblinding, by removing all event data after the date of the SUSAR unblinding from the analysis.

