/* cnsr(1): value 1 indicating censored observations*/  
proc phreg data=data1;  
  model OS * CNSR(1) = TRTGRP covariate1 covariate2 covariate3  
  /ties=exact;  
  strata randomization_strata;  
  output out=outdata ressch= s_TRTGRP s_covariate1 s_covariate2  
  s_covariate3;  
run;
```

```
proc sgplot data=outdata;  
  scatter y=TRTGRP x=OS/ name="Schoenfeld_&CHECK";  
  loess y=TRTGRP x=OS /SMOOTH=.8 DEGREE=1 INTERPOLATION= CUBIC ;  
run;
```

[figure not shown]
Note: Repeat proc gplot for other covariates (covar1, covar2, etc.);

C.10 Kaplan Meier Method: Stratified Log-Rank Test and Standard Errors Using Greenwood's Formula

```
/* cnsr(1): value 1 indicating censored observations */  
proc lifetest data=data1;  
    time Days*cnsr(1);  
    strata <stratum> / group=TRTGRP;  
run;
```

C.11 Stratified multivariate Cox Proportional Hazards Model

```
/* cnsr(1): value 1 indicating censored observations */  
proc phreg data=dat1;  
    model OS * CNSR(1) = TRTGRP covariate1 covariate2 / ties=exact  
    rl=pl;  
    strata <stratum>;  
run;
```

C.13 Inverse Probability Censoring Weighting (IPCW)

```
*** Model 1: time-independent model
*** model the probability of without subsequent anti-cancer therapy per
each subject
*** include the baseline covariates;
proc sort data=adsl out=indep;by subther;run;
proc genmod data=indep order=data;
  class disstgi LDH brafmud PDL1;
  model subther = disstgi LDH SLD brafmud PDL1 / dist=binomial
link=logit ;
  output out=num prob=num;
run;

*** Model 2: time-dependent model
*** model the probability of without subsequent anti-cancer therapy per
each subject-timeinterval
*** include both baseline covariates and time-dependent covariates;
proc sort data=all2 out=dep;by subther;run;
proc genmod data=dep order=data;
  class disstgi LDH brafmud PDL1 <time-dep categorical vars> ;
  model subther = disstgi LDH SLD brafmud PDL1 <time-dep vars> /
dist=binomial link=logit ;
  output out=den prob=den;
run;

proc sort data=num ;by usubjid;run;
proc sort data=den ;by usubjid;run;

data wgt;
retain <stratification factors> armcd usubjid subther
      num den
;
  merge num den ;
  by usubjid;
run;

*** calculate weights;
data wgt2;
  set wgt;
  by usubjid;

retain w_num w_den ;
  if first.usubjid then do;
    w_num = 1;
    w_den = 1;
  end;
  w_num = w_num*num ;
  w_den = w_den*den ;

  if subther = 'y' then weights = (1-w_num)/(1-w_den);
  else if subther = 'n' then weights = w_num/w_den;
run;

data os_wgt;
  merge wgt2 (in=a)

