        os (in=b)
;
;
```

```
by usubjid;  
if a and b;  
run;
```

```
*** Inverse Probability Censoring Weighted Cox model ;  
proc phreg data=os_wgt;  
class armcd(ref='PB_PEM');  
model aval*cnsr(1)=armcd;  
strata <stratification factors>;  
freq weights / nottruncate;  
hazardratio armcd / alpha=0.05 cl=wald diff=ref;  
ods output hazardratios=hr_ci_ipcw;  
run;
```

C.14 Gail and Simon Quantitative and Qualitative Interaction Tests and Post Hoc Power Test

```
%macro int(ds      =, /* Dataset                               */
           txvar   =, /* Treatment indicator                   */
           sgroup  =, /* Subgroup variable                                         */
           time    =, /* Time to event variable                                    */
           censor  =, /* Censor var 1=observed 0=censored                         */
           covar   =, /* Covariates for model                                     */
           alpha   =, /* 2-sided nominal alpha for power                         */
           outf    =  /* SASname of results file                                 */ );

proc sort data=&ds out=&ds._d1;
  by &sgroup;
run;

/*
proc printto new print=&outf; run;
*/
ods output ParameterEstimates=phfit;
proc phreg data=&ds._d1;
  model &time*&censor(0)=&txvar &covar
  / rl ties=exact;
  by &sgroup;

data ph (keep=&sgroup estimate v rename=(estimate=b));
  set phfit (keep=&sgroup estimate stderr);
  v=stderr**2;

proc transpose data=ph prefix=b out=b (drop=_name_);
  var b;
proc transpose data=ph prefix=v out=v (drop=_name_);
  var v;

data t; merge b v;
  label H='(GS)|Quant.|Test|Value'
        ph='(GS)|Quant.|p-val' ph_p='(GS)|Quant.|Post Hoc|Power'
        Q='(GS)|Qual.|Test|Value' pq='(GS)|Qual.|p-val'
        pp='(PG)|Qual.|p-val' Qmin='(PG)|Qmin' Qmax='(PG)|Qmax'
        alpha='Alpha|2-tail';
  alpha = &alpha+0;
  array b b1-b30;
  array v v1-v30;
  g=0; do i=1 to 30; if b{i} ne . then g+1; end;

  * (GS) Quantitative interaction test ;
  n=0; d=0;
  do i=1 to g; n=n + b{i}/v{i}; d=d + 1/v{i}; end;
  Dbar=n/d;
  H=0;
  do i=1 to g; H=H + ((b{i}-Dbar)**2)/v{i}; end;
  ph=1-probchi(H,g-1);

[figure not shown]
  * Post hoc power ;
  c_alpha = quantile('CHISQ', 1-alpha, g-1);
  ph_p = 1 - probchi(c_alpha, g-1, H);

[figure not shown]
  * (GS) Qualitative Interaction ;
```

[figure not shown]
```
Q=0; Qn=0; Qp=0; pq=0;
do i=1 to g;
  Qn=Qn + ((b{i}**2)/v{i})*resolve(b{i}>0);
  Qp=Qp + ((b{i}**2)/v{i})*resolve(b{i}<0);
end;

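### The IPCW code in SAP Appendix C.13 does not carry out the method described in 10.5.4.2, and its estimate and confidence interval cannot be relied on

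*SAP*

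**What the plan says.** SAP 10.5.4.2 assesses the effect of later anticancer treatment on OS in several ways: incidence and timing by arm, time to first use, and OS censored at the first selected therapy. Because that censoring may depend on prognosis, "the OS effect will also be estimated with an inverse probability censoring weighting (IPCW) method", drawing on covariate history and "outcomes up to the start of subsequent anti-cancer therapy". SAP 10.5.4 sets the status of all these analyses: "All p-values will be descriptive".

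Appendix C.13 holds the only code given for the method:

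- **Numerator (Model 1).** It is fitted on the subject-level file, "proc sort data=adsl out=indep;by subther;run", and returns one probability per subject, "output out=num prob=num".
- **Denominator (Model 2).** It is fitted on one row per subject and time interval, with baseline and time-dependent covariates.
- **Weights.** The two outputs are merged by subject and both are multiplied down the interval rows. The weight is their ratio, except on the row where therapy starts: "if subther = 'y' then weights = (1-w_num)/(1-w_den" (closing bracket cut).
- **Outcome model.** All rows are merged with the OS file by subject. PHREG then fits "model aval*cnsr(1)=armcd", with the weights entered through a FREQ statement, and the interval comes from "hazardratio armcd / alpha=0.05 cl=wald diff=ref". The step has no start time, no ID statement and no robust covariance option.

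**The concern.** An IPCW analysis follows each subject in short intervals up to the start of therapy, censors there, and reweights those still under observation by the inverse of their probability of not yet having been censored. The weight must vary with time and use only the past. The variance must allow for one subject contributing many weighted rows. C.13 appears to miss each of these requirements.

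IPCW is included because simple censoring at therapy is acknowledged to be open to bias. If the code does not remove that bias, or adds to it, the report would show a figure labelled as the correction that is not one. Readers would have no sound basis for judging whether later therapy changes the OS result.

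**Working it through.** The plan gives no numerical IPCW result to reproduce. The check is a trace of C.13, arithmetic on the weights, and simulation.

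**1. Repeated rows.** The weight file has one row per subject-interval, and nothing reduces it before the merge with `os`. If `os` has one record per subject (the natural reading, though not stated), every interval row carries the same time T, status d and arm x. The weighted partial log-likelihood (Breslow ties) then depends only on W_i, the sum of subject i's row weights:

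l(β) = Σ_i d_i W_i [βx_i − log Σ_{j: T_j ≥ T_i} W_j exp(βx_j)]

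This is a fit with one row per subject and one fixed weight, applied from time zero but determined by how long the subject was later followed. In one simulated trial, the 8434 interval rows (214 deaths before therapy appearing as 2202 event rows) and the collapsed 692-row fit gave the same log HR, 0.104357, and the same SE, 0.064069.

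**2. Numerator.** Let p be the whole-study probability of no therapy, spread equally over 10 intervals, with therapy unrelated to prognosis. Correct stabilised weights are then all 1. In C.13, row k has w_num = p^k and w_den = p^(k/10), so the weight is p^(0.9k).

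- p = 0.6: 0.6^0.9 = 0.631; 0.6^4.5 = 0.100; 0.6^9 = 0.010.
- At k = 10, for p = 0.5 to 0.8: 0.5^9 = 0.002 to 0.8^9 = 0.134.
- A death in interval 10 counts as Σ p^(0.9k) over k = 1 to 10, with r = 0.6^0.9: r(1 − r^10)/(1 − r) = 0.631 × 0.990/0.369 = 1.70 deaths. For p = 0.5 to 0.8 this is 1.15 to 3.89.

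**3. Therapy row.** In the same example its weight is (1 − 0.6^k)/(1 − 0.6^(k/10)):

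- k = 1: 0.400/0.0498 = 8.03
- k = 5: 0.922/0.225 = 4.09
- k = 10: 0.994/0.400 = 2.48

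This is added to the subject's total. If `os` is censored at therapy, subjects who start therapy bring in heavily weighted event-free time, which lowers the apparent hazard in the arm treated more.

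**4. Simulation.** N = 692 is from SAP Table 5. The 26-month accrual and month-75 cutoff are from protocol Table 9. Assumed:

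- 3-month intervals, by analogy with the 12-week intervals in 10.5.4.1
- one binary prognostic covariate
- therapy almost only after progression, with 38% to 63% treated
- therapy effect on death of HR 0.6

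There were 600 replicates per scenario and 342 to 377 deaths. Truth is the no-therapy HR from 300,000 simulated subjects. With `os` censored at therapy, mean HR (95% CI coverage):

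| Scenario | True HR | Simple censoring | C.13 | Correct IPCW |
|---|---|---|---|---|
| Control treated more | 0.745 | 0.872 (81%) | 1.168 (17%) | 0.741 (96%) |
| Same, null | 1.008 | 1.201 (74%) | 1.693 (10%) | 0.997 (96%) |
| Equal post-progression rates | 0.745 | 0.706 (95%) | 0.696 (81%) | 0.732 (97%) |
| Same, null | 0.997 | 0.994 (95%) | 0.987 (84%) | 0.999 (95%) |

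If `os` is not censored at therapy, the mean C.13 HR is near the truth (0.756 and 0.769 with an effect; 0.997 and 0.992 under the null). Coverage is then 23% to 29%, because the reported SE is 0.058 to 0.062 against a real SD of 0.306 to 0.351.

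**5. Attribution.** Without the therapy row, C.13 returns the simple-censoring HR within 0.002 (0.873 against 0.872; 1.202 against 1.201), so the repeated rows give no correction. The therapy-row weight produces the large shifts. The numerator error alone mainly costs precision (robust SE 0.301 to 0.336 against 0.131 to 0.151).

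**6. Direction of the CI error.** A second simulation used n = 660, 12-week intervals, 300 trials per setting and therapy without effect on death.

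- With conditional HR 0.70 and 35% treated, the C.13 SE was 0.098 against an SD of 0.149, with coverage 83% (77% at conditional HR 1.0).
- With 71% treated, the SE was 0.266 against an SD of 0.215, so the interval was too wide.
- The correct analysis at 35% treated gave HR 0.647 (target 0.649), SE 0.130, SD 0.128 and coverage 94%.

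**The case against.** C.13 is a code fragment with placeholders in a supplemental appendix, and the governing text in 10.5.4.2 is sound. Neighbouring fragments are plainly unadapted templates: C.8 models LRFS, C.16 labels an arm GM-CSF, and C.17 uses PFS with a fixed 2018 cutoff. SAP 9.7 provides for program verification. The files `all2` and `os` are not defined. If `os` held interval rows, the merge would pair them by position and a death might be flagged once, so the row-collapse result would not apply. No document gives therapy rates, and the near-reversal of the HR depends on assuming more therapy on control. With equal rates the point estimate moves little beyond simple censoring. In the second simulation, clustering alone brought coverage to 94%, with HR 0.631 against a target of 0.649. Other analyses of subsequent therapy are planned, and all are descriptive.

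Much of this stands as a limit on size. The exact form of the row defect depends on `os`, and the simulated HRs are illustrative. It does not rescue the code. The placeholders cover covariates and stratification factors, not the merge, the cumulation, the weight formula or the model statement. If `os` had interval rows, the missing start time would still put every row at risk from time zero. General verification language does not correct a specified formula, and no other SAP text available here does so.

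**Conclusion.** The concern holds. C.13 does not implement the IPCW analysis described in 10.5.4.2. Confidence is high for the code defects, which can be read directly: no (start, stop] times, a whole-study numerator multiplied in on every row, a non-standard weight on the therapy row, and a model-based interval without clustering.

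The size depends on the data. Under independent therapy start with p = 0.6 over 10 intervals, weights fall to 0.010 where 1 is correct. In the four 3-month scenarios, C.13 coverage was 10% to 84% with `os` censored at therapy and 23% to 29% without. With 1-month intervals (200 replicates) it was 4% to 77% and 15% to 22%. With heavy therapy use (80% to 87% treated, `os` censored) the interval was too wide (SE 0.514 against SD 0.317). These HRs and coverages rest on assumed therapy rates and effect.

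The consequence is confined to a descriptive sensitivity analysis. The correction should be made, but neither the primary OS test nor Type I error is affected.

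**What to change.** Replace C.13 before the study team is unblinded:

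- Fit pooled logistic models on the same interval rows for both parts of the weight. The numerator has arm, interval and baseline covariates, and any baseline covariates kept there also go into the Cox model. The denominator adds the time-dependent covariates.
- Cumulate both within subject, censor at the start of therapy, and drop the separate therapy-row weight.
- Fit the Cox model on one row per interval with (tstart, tstop) and an interval-specific event flag, using WEIGHT in place of FREQ, with COVS(AGGREGATE) and ID usubjid.
- State the interval length and the layout of `all2` and `os`.

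The cost is one replaced code fragment, with no new data. The reported interval may become wider or narrower.

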10.5.5 Additional Summaries

CR per BICR, and separately DpR per BICR, will be summarized for the Full Analysis Set. The proportion of subjects in each response level (CR analysis response levels: CR vs non-CR; DpR analysis response levels: G4/G5 vs G0/G1/G2/G3) will be provided by treatment arm. The between-treatment arm differences in proportions will be calculated and 95% CIs will be estimated using Wilson's score method for continuity correction.

Additionally, OS will be summarized by CR response level (CR vs non-CR) per BICR and treatment arm as well as by DpR response level (G4/G5 vs G0/G1/G2/G3) per BICR and treatment arm for the Full Analysis Set. The OS KM median estimates with the associated 95% CIs will be summarized for each level of the response within treatment arm.

